### **3.6 Triggering of treatment costs on randomisation to an EVAR device**

The use of stents over open repair carries a significant increase in treatment costs. Following negotiations with The NHS Executive (North Thames London Region) it was agreed that treatment costs may be reimbursed to each trial centre on randomisation for an EVAR device. Service costs are unlikely to be funded. An assessment of costs was carried out to ascertain the excess treatment cost expenditure associated with an EVAR repair over an open repair (OR) or best medical treatment. According to Hölzzenbein *et al* 80% of costs associated with AAA repair can be accounted for by, 1) total length of stay, 2) days in ITU, days in HDU, 3) theatre costs. Estimates were made and are given in Figures 5 and 6. Thus, a patient randomised for EVAR in EVAR Trial 1 will require £6,465 additional funding triggered to the relevant NHS provider Trust on a named patient, named operator and named centre basis. Similarly, a patient randomised to EVAR in EVAR Trial 2 will require £9,139 of triggered funding.

### **3.7 Financial provision for complete data collection**

It is essential that high quality data is collected for all patients randomised in the EVAR Trials. To encourage good data retrieval, trial co-ordinators based at each of the 13 participating centres will be paid an additional amount of money on receipt of clean and complete data at Charing Cross. An estimate has been made of the length of time a trial co-ordinator will take to complete the case report forms, (1 hour for a baseline assessment and 20 minutes for a follow up appointment). A £25 payment will be made for each complete baseline assessment and a further £25 payment for the operation data. A £25 payment will also be made on receipt of each complete set of follow-up data.

Treatment costs	EVAR	OR
Theatre, surgeon, anaesthetist, nurse, sutures, current device *	3.7 hours = £924	3.7 hours = £924
AAA repair device **	£5,000	0
Wires, catheters for radiologists **	£800	0
Consultant radiologist *** (2 day)	£378	0
Senior radiographer grade I *** (2 day)	£146	0
Radiology nurse, Grade F *** (2 day)	£141	0
Post operative CT scans (£250 each) at 1/12, 3/12, 6/12, 1, 2, 3, 4 years	£1,750	£1,750
Totals	£9,139	£2,674

Net treatment cost for EVAR 2 = £9,139  
(70 randomised per year => 35 for EVAR)

Net treatment cost for EVAR 1 = EVAR - OR  
= 9,139 - 2,674 = £6,465  
(200 randomised per year => 100 for EVAR)

\* taken from "Resource use and costs of elective surgery for asymptomatic abdominal aortic aneurysm" R.G. Jepson, J.F. Forbes, F.G.R. Fowkes  
European Journal of Vascular and Endovascular Surgery, 1997, Vol 14.

\*\* Manufacturers price lists

\*\*\* NHS salary scales 1998

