#### **4.2 The incidence of endoleaks from EVAR (Safety of Procedure)**

A CT scan is performed on all EVAR patients in the first month after operation seeking endoleak. Endoleak is extremely important to find particularly at the top end where blood flow between the stent graft system and the aortic wall can increase pressure on the aortic wall, greater than if the stent graft system was not in place. If uncorrected, mortality follows. Endoleak is checked at the time of the procedure with contrast radiography but if the upper end works loose, endoleak from there could occur and is best detected (at this state of knowledge) by CT scan with contrast. Additional procedures to correct endoleak such as the use of additional stents with covered grafts will be carefully noted. This is an important outcome measure and critical to assure safety and efficacy of the procedure. It will also affect costs and patient anxiety. Endoleak is conveniently classified in the manner suggested by Geoffrey White of Sydney, Australia :

Endoleak type I	Perigraft leak at proximal or distal end
Endoleak type II	Retrograde endoleak from patent lumbar artery, inferior mesenteric artery, intercostal artery or other (renal, internal iliac, subclavian etc.)
Endoleak type III	Fabric tear
Endoleak type IV	Graft porosity
Endoleak type V	Endopressure

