The portfolio of instruments to measure HRQL in the proposed trials is designed to be comprehensive yet brief. It will be completed by patients in the form of a questionnaire - at recruitment and subsequently one, three and 12 months after surgery or the beginning of medical treatment as appropriate. The questionnaire will include two generic instruments - the Short-Form 36-item (SF-36) Health Survey and the EuroQol. The SF-36 is a health profile comprising eight distinct scales including physical and social functioning, role limitation, mental health, vitality, pain and general health. It has been shown to be valid, reliable and responsive to changes in health in British patients. The EuroQol is a validated utility measure comprising five items covering mobility, self care, usual activities, pain, anxiety and depression. The HRQL states defined by the various combinations of responses to these items have been valued by the general public for use in cost-utility analysis. Unfortunately we know of no specific instrument designed to measure HRQL in patients suffering from AAA; this has been confirmed by a recent systematic search of Medline. One likely reason for this lack is the wide range of effects that this condition has on patients. In these circumstances we propose to use the State Trait Anxiety Inventory (STAI) which encompasses both the state form (transitory feelings of fear or worry) and the trait form (the stable tendency to respond anxiously to stressful situations or proneness). The STAI measures in-built tendency to anxious response and current feelings of anxiety. It enables the investigator to distinguish between the transitory (state) and the dispositional types of anxiety.

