#### **4.5 Follow-up**

All trial patients will be ONS flagged for mortality. HRQL data will be collected at 1, 3 and 12 months following treatment for those allocated to an operation. However, for patients randomised to best medical treatment in EVAR Trial 2 we have incorporated a 1 month delay for the early follow-up in these patients. This takes into account the estimated 1 month delay patients will experience waiting for their EVAR procedure in the EVAR arm of trial 2.

Cost evaluation will be based on operation costs and in patient admissions during the course of follow up. The incidence of any adverse events will also be collected at every follow-up appointment, eg. tender AAA, ruptured AAA, conversion to open repair, myocardial infarction, stroke, renal failure and amputation. CT scan will be used for assessment of growth rates, persistent endoleaks and durability which could vary with stent graft type. CT scan follow-up will be at 1 and 3 months, 1 year, 2 years, 3 years and 4 years for EVAR patients in trial 1 or 2. CT scan follow up will be performed annually for patients randomised to EVAR Trial 1 OR. CT scan follow up will be annually for best medical treatment patients in EVAR Trial 2. Creatinine will be recorded annually for all patients to assess any changes in renal function between the randomised groups.

[figure not shown]
Figure 8 illustrates the treatment procedure for each patient.

*Figure 8 – Patient treatment procedure within EVAR Trials*

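### Figure 5 costs seven follow-up CT scans for both EVAR and OR, but Section 4.5 schedules six after EVAR and annual scans in the comparators, so the sums triggered in 3.6 do not match the follow-up, and the 4.5 cost sentence leaves surveillance CT out

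*Protocol*

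**What the plan says.** **Costing.** Figure 5, printed after the text of Section 3.7, has one row for follow-up imaging: "Post operative CT scans (£250 each) at 1/12, 3/12, 6/12, 1, 2, 3, 4 years". That is seven scans, entered as £1,750 in both the EVAR and the OR column. The column totals are £9,139 and £2,674. Section 3.6 uses the difference, £6,465, as the additional funding triggered per EVAR patient in Trial 1, and £9,139 as the sum triggered per EVAR patient in Trial 2.

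**Follow-up.** Section 4.5 sets the scans by arm:
- EVAR, either trial: "CT scan follow-up will be at 1 and 3 months, 1 year, 2 years, 3 years and 4 years for EVAR patients".
- OR, Trial 1: "CT scan follow up will be performed annually for patients randomised to EVAR Trial 1 OR".
- Best medical treatment, Trial 2: "CT scan follow up will be annually for best medical treatment patients in EVAR Trial 2".

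**Cost evaluation.** Section 4.5 also says "Cost evaluation will be based on operation costs and in patient admissions during the course of follow up". Section 4.4 says that NHS costs will be collected and gives a list that includes hospital stay and theatre costs. Tests appear there only as a component of theatre costs. Neither section names follow-up CT.

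**The concern.** The table that sets the reimbursement and the section that sets the follow-up describe different scan schedules. Figure 5 has a 6-month scan that 4.5 lacks, and it gives OR patients the same early scans as EVAR patients, whereas 4.5 gives them annual scans only. Because Figure 5 charges CT equally to both columns, CT cancels from the Trial 1 net, and the heavier imaging that 4.5 requires after EVAR goes unfunded in that sum.

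The cost evaluation raises a related question. Under 4.5, surveillance CT is used more after EVAR than in either comparator. A cost comparison limited to operations and in-patient admissions would leave that difference out, in a trial that sets out to compare costs.

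**Working it through.** **Inputs.** From Figure 5: theatre £924 (both columns); for EVAR only, device £5,000, wires and catheters £800, radiologist £378, radiographer £146 and radiology nurse £141; CT £250 per scan; 100 EVAR patients a year in Trial 1 and 35 in Trial 2. From Figure 6: service costs of £3,523 (EVAR) and £2,430 (OR). From 4.5: the scan schedules.

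**1. Reproduce the stated figures.**
- EVAR without CT: 924 + 5,000 + 800 + 378 + 146 + 141 = £7,389. OR without CT: £924.
- EVAR with seven scans: 7,389 + 7 × 250 = £9,139, as stated.
- OR with seven scans: 924 + 7 × 250 = £2,674, as stated.
- Trial 1 net: 9,139 − 2,674 = £6,465, as stated.

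The totals reproduce only with seven scans in each column.

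**2. Apply the 4.5 schedule over Figure 5's four years.** EVAR has 6 scans (1 and 3 months; 1, 2, 3 and 4 years). Each comparator has 4.
- EVAR: 7,389 + 6 × 250 = £8,889.
- OR: 924 + 4 × 250 = £1,924.
- Trial 1 net: 8,889 − 1,924 = £6,965. Shortfall: 6,965 − 6,465 = £500, and 500 / 6,465 = 7.7%.
- Trial 2, full EVAR cost: £8,889. Excess: 9,139 − 8,889 = £250, and 250 / 9,139 = 2.7%.
- Trial 2, net of the control arm's annual scans: 8,889 − 4 × 250 = £7,889. Excess: 9,139 − 7,889 = £1,250, and 1,250 / 9,139 = 13.7%.

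**3. Dependence on the horizon.** Over a shared follow-up of H whole years (H = 1 to 4), EVAR has 2 + H scans and the comparator has H. The difference is always two scans, 2 × 250 = £500. The two net figures therefore do not depend on H: 7,389 − 924 + 500 = £6,965 and 7,389 + 500 = £7,889. The full EVAR figure of £8,889 does assume four years.

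**4. Scale at Figure 5's volumes.** Trial 1: 100 × £500 = £50,000 a year too little. Trial 2: 35 × £250 = £8,750 a year too much on the full basis, or 35 × £1,250 = £43,750 on the net basis.

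**5. Cost evaluation without follow-up CT, on the 4.5 schedule and before deaths.** The omitted CT is 6 × 250 = £1,500 after EVAR and 4 × 250 = £1,000 in each comparator, so EVAR's extra cost is understated by £500 per patient. In Trial 1 the protocol's own estimates without follow-up CT already make EVAR dearer: (7,389 − 924) + (3,523 − 2,430) = 6,465 + 1,093 = £7,558. Counting CT gives £8,058. The direction does not change.

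**The case against.** **Figure 5 is a budget estimate and does not direct care.** This stands, and it settles which text governs. Section 4.5 is the follow-up section and states by arm what will be done, while 3.6 introduces the costing as estimates. Other text fits 4.5. Section 4.2 ties the early scan to EVAR and endoleak ("A CT scan is performed on all EVAR patients in the first month after operation seeking endoleak"). The quality-of-life contacts in 4.5 ("HRQL data will be collected at 1, 3 and 12 months following treatment") and 4.3 ("at recruitment and subsequently one, three and 12 months after surgery") also have none at 6 months. A reader might infer that the protocol leaves the schedule undecided, or that a centre cannot tell which scans its payment covers. The documents do not support that: 3.6 triggers one sum at randomisation and describes no scan-by-scan claim. Figure 8, which illustrates the treatment procedure, is not shown and could not be checked.

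**Nothing is mis-added.** This stands. The discrepancy is between two schedules; the sums themselves are correct.

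**CT is not excluded from the economic evaluation.** This stands in part. The list in 4.4 is open, and itemising resources can be left to an analysis plan. A reader might infer that the protocol rules surveillance CT out, or that the Figure 5 mismatch itself biases the cost-effectiveness result. Neither follows: CT is unnamed rather than excluded, and Figure 5 is a reimbursement estimate outside the economic analysis. What remains is that the 4.5 cost sentence names two sources of cost, and scheduled follow-up CT is neither.

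**The Trial 2 sum depends on its basis.** This stands. Figure 5 labels £9,139 as net but subtracts nothing, and its caption presents it as the full EVAR cost. Section 3.6, however, says the assessment sought the excess over OR or best medical treatment. Both £8,889 and £7,889 therefore have to be shown. Setting Figure 5's seven EVAR scans against 4.5's annual control scans would give a larger Trial 2 difference, but the protocol specifies no such pairing.

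**Conclusion.** The mismatch is real and minor. Taking 4.5 as the governing schedule, the Trial 1 sum should be £6,965, so £6,465 is £500 (7.7%) too low. This holds over any shared follow-up of one to four whole years. The Trial 2 sum should be £8,889 as a full EVAR cost over four years, or £7,889 net of control scans, against £9,139 stated.

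Separately, a cost evaluation that follows the 4.5 sentence as written understates EVAR's extra cost by up to £500 per patient. That figure is before deaths: a death within three months of the procedure removes early scans, and a survival difference between arms would alter the annual counts. It assumes the £250 unit cost and adherence to 4.5. It does not change which arm costs more on the protocol's estimates, and mortality endpoints, sample size and stopping are unaffected.

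**What to change.** 1. Align Figure 5 with the 4.5 schedule (six scans after EVAR, four annual scans after OR) and restate the Trial 1 sum in 3.6 as £6,965. If the 6-month scan and the early OR scans are in fact intended, add them to 4.5 instead.
2. State whether the Trial 2 sum is the full EVAR cost (£8,889) or the excess over best medical treatment (£7,889), and label it accordingly.
3. Amend the cost sentence in 4.5 to count follow-up CT actually performed in every arm at £250 per scan.

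The cost is an edit to one table and two sections, agreement of the revised sums with the funder, and one more resource item in the cost evaluation, using scans already scheduled and a unit cost already stated. No extra patient contact is needed unless the additional scans are intended.

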**Figure 5 -Treatment costs of EVAR (EVAR Trial 2) and net costs over OR (EVAR Trial 1)**

Service costs	EVAR	OR
Pre operative duplex and CT scans *	£513	£513
Pre operative assessment days ** (standard rate, £112 per day) *	2 days = £224	1 day = £112
Post operative ITU days ** (standard rate, £797 per day) *	0	1 day = £797
Post operative HDU days ** (standard rate, £398 per day) *	7 days = £2,786	0
Post operative standard days ** (standard rate, £112 per day) *	0	9 days = £1,008
Totals	£3,523	£2,430

Net service cost for EVAR 2 = £3,523

Net service cost for EVAR 1 = EVAR - OR  
= 3,523 - 2,430 = £1,093

\* taken from “Resource use and costs of elective surgery for asymptomatic abdominal aortic aneurysm” *R.G. Jepson, J.F. Forbes, F.G.R. Fowkes* European Journal of Vascular and Endovascular Surgery, 1997, Vol 14.

\*\* taken from “UK Small Aneurysm Trial” papers  
Lancet 21st November 1998

We are extremely grateful to [name] for suggestions, particularly with respect to building in stopping rules, during trial monitoring. She suggested we take the control group mortality as 25% per annum and assume the expected between group relative difference of around 45% (absolute difference of around 20%) using a 2 tail test to allow for both a possible benefit or possible adverse effect of EVAR. At 90% power and 1% alpha we need around 734 patient years. Alpha is increased to take account informally of 3 looks which would overall give a lower alpha. This can be achieved by randomising 300 patients over 4 years and assuming an average follow-up per patient of 2.5 years with a further minimum one year follow-up to achieve the required number of patient years. If we randomise more patients earlier then we will accrue more patient years more quickly. Then assuming an overall death rate of 30% in the 2 groups if EVAR is worse by 20% or if EVAR is better we will have between 150 to 225 deaths. We could then plan 3 looks based on 75 deaths with stopping rules built in. However if the mortality is lower because EVAR is better we will not get this number of deaths. It would be "safer" to recruit more patients from the outset. If we could recruit 440 patients over the 4 years then we could accumulate 1,000 patient

Sample size calculations are calculated to provide 90% power at the 5% significance level.

	Open repair [UK Aneurysm Trial]	EVAR [Original grant application]	EVAR [RETA 1996 data]	EVAR [RETA 1997 data]	EVAR [RETA 1998 data]
Number dead at 30days Total operated	$\frac{11}{191}$	$\frac{6}{91}$	$\frac{8}{96}$	$\frac{4}{126}$	$\frac{2}{180}$
30 day operative mortality	5.76 %	6.6 %	8.3 %	3.2 %	1.1 %
Numbers required per group (total recruitment) to detect difference between EVAR and OR		17,504 (35,008)	2,205 (4,410)	1,448 (1,896)	361 (722)

In favour of OR

In favour of EVAR

Figure 7 – Numbers of patients required for EVAR Trial 1 to detect a difference in 30 day operative mortality between Open Repair (OR) at 5.76% and EVAR mortality figures according to year of RETA audit.

years (especially with fast and early patient recruitment) then 3 looks could be carried out every 100 deaths. This would also preserve a higher alpha value over the looks. So we would not need to wait 4 years to start the first analyses, it would depend entirely on the accrual of death and patient years. We should get the first 300 or so patient years by year 3. The monitoring committee would check (1) patient recruitment (2) deaths and advise the Steering Committee of any adjustments for recruitment etc. as necessary.

#### **4.2 The incidence of endoleaks from EVAR (Safety of Procedure)**

A CT scan is performed on all EVAR patients in the first month after operation seeking endoleak. Endoleak is extremely important to find particularly at the top end where blood flow between the stent graft system and the aortic wall can increase pressure on the aortic wall, greater than if the stent graft system was not in place. If uncorrected, mortality follows. Endoleak is checked at the time of the procedure with contrast radiography but if the upper end works loose, endoleak from there could occur and is best detected (at this state of knowledge) by CT scan with contrast. Additional procedures to correct endoleak such as the use of additional stents with covered grafts will be carefully noted. This is an important outcome measure and critical to assure safety and efficacy of the procedure. It will also affect costs and patient anxiety. Endoleak is conveniently classified in the manner suggested by Geoffrey White of Sydney, Australia :

Endoleak type I	Perigraft leak at proximal or distal end
Endoleak type II	Retrograde endoleak from patent lumbar artery, inferior mesenteric artery, intercostal artery or other (renal, internal iliac, subclavian etc.)
Endoleak type III	Fabric tear
Endoleak type IV	Graft porosity
Endoleak type V	Endopressure

#### **4.3 Health Related Quality of Life (HRQL)**

In measuring HRQL a combination of specific and generic instruments is recommended e.g. . Specific instruments are useful for clinical evaluation; their narrow focus makes them more responsive to small but clinically important changes in health. Generic instruments are useful for economic evaluation and for comparisons across groups of patients; their comprehensive nature also enables them to detect unforeseen effects of treatment. There are two main types of generic instrument - health profiles and utility measures. Health profiles measure HRQL across a number of distinct dimensions and thus assess the effect of health care on different aspects of HRQL. Utility measures incorporate the values that individuals

attach to HRQL and thus produce a single index of HRQL suitable for economic evaluation.

The portfolio of instruments to measure HRQL in the proposed trials is designed to be comprehensive yet brief. It will be completed by patients in the form of a questionnaire - at recruitment and subsequently one, three and 12 months after surgery or the beginning of medical treatment as appropriate. The questionnaire will include two generic instruments - the Short-Form 36-item (SF-36) Health Survey and the EuroQol. The SF-36 is a health profile comprising eight distinct scales including physical and social functioning, role limitation, mental health, vitality, pain and general health. It has been shown to be valid, reliable and responsive to changes in health in British patients. The EuroQol is a validated utility measure comprising five items covering mobility, self care, usual activities, pain, anxiety and depression. The HRQL states defined by the various combinations of responses to these items have been valued by the general public for use in cost-utility analysis. Unfortunately we know of no specific instrument designed to measure HRQL in patients suffering from AAA; this has been confirmed by a recent systematic search of Medline. One likely reason for this lack is the wide range of effects that this condition has on patients. In these circumstances we propose to use the State Trait Anxiety Inventory (STAI) which encompasses both the state form (transitory feelings of fear or worry) and the trait form (the stable tendency to respond anxiously to stressful situations or proneness). The STAI measures in-built tendency to anxious response and current feelings of anxiety. It enables the investigator to distinguish between the transitory (state) and the dispositional types of anxiety.

We also propose to use The Patient Generated Index (PGI). This is a quasi-specific HRQL instrument that focuses on the concerns of the *individual* patient with a given condition rather than concerns derived by the investigator for the *typical* patient with that condition. Patients nominate and rate on a scale the five most important aspects of their lives affected by their health. The final score represents the gap between their current health status and their expectations in those areas of their lives in which they would most value an improvement. Thus the PGI measures the effect of the condition on quality of life as defined by the patient. There is good evidence for the acceptability, validity, reliability and responsiveness of this instrument.

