#### 4.4 Economic Evaluation

Within each of the two sub-trials the type and extent of economic evaluation will depend crucially upon the clinical outcome of that trial:

1. If one technology produces a clinically better outcome than another at significantly lower cost, then clinical and financial criteria both lead to the same conclusion.
2. If there is no clinically significant difference in outcome between two technologies under comparison, then the least cost option is preferable (cost minimisation analysis).
3. If one technology produces a clinically better outcome than another at higher cost, then we shall undertake marginal cost-utility analysis (based on mortality and the EuroQol) and, if appropriate, marginal cost-effectiveness analysis (based on the Patient Generated Index (PGI)).

NHS costs will be collected. These will include the length of time in hospital (subdivided into intensive care, high dependency care, acute care and convalescent care), and theatre costs (subdivided into the length of operation and the use of staff, tests and drugs).

Under scenario 3 we shall use the EuroQol to estimate changes in health utility. One advantage of using the EuroQol is that it expresses changes in HRQL on a ratio scale. Thus cost-utility ratios in the form of cost per quality-adjusted life year (QALY) can be constructed from changes in mortality (if any) and in HRQL. Comparisons can then be made with other health care interventions. If there is no significant change in mortality, however, care will be needed because the EuroQol is less responsive to change than most condition-specific measures. To reduce the possibility of a Type II error, we shall also undertake a cost-effectiveness analysis based on the PGI.

We shall subject our results to extensive sensitivity analysis. First we shall identify the critical components of the cost and outcome by varying all estimated parameters in the analysis individually, to see how the economic findings are affected. Those parameters which lead to substantial changes in these findings will be varied over plausible ranges in combination to see whether the main conclusions are altered.

[figure not shown]

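### EuroQol collection ends at 12 months while deaths, in-patient costs and device durability are followed to about 4 years, so a cost per QALY beyond year 1 would have no measured utility behind it

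*Protocol*

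**What the plan says.** Protocol section 4.3 sets the quality-of-life questionnaire, which contains the EuroQol, "at recruitment and subsequently one, three and 12 months after surgery", or after the start of medical treatment where that applies. Section 4.5 repeats the schedule: "HRQL data will be collected at 1, 3 and 12 months following treatment for those allocated to an operation". It adds a one-month shift of the early follow-up for the medical arm of Trial 2. Neither section plans a later measurement.

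The other components run longer (all section 4.5):

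- Deaths: "All trial patients will be ONS flagged for mortality", with no end date.
- Costs: "Cost evaluation will be based on operation costs and in patient admissions during the course of follow up".
- Device durability: "CT scan follow-up will be at 1 and 3 months, 1 year, 2 years, 3 years and 4 years for EVAR patients". The open-repair arm of Trial 1 and the medical arm of Trial 2 have annual CT.
- Renal function: "Creatinine will be recorded annually for all patients to assess any changes in renal function between the randomised groups".
- Adverse events: recorded at each follow-up appointment.

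Section 4.4 says that "cost per quality-adjusted life year (QALY) can be constructed from changes in mortality (if any) and in HRQL". It commits to this analysis only in its third scenario, a better outcome at higher cost. It gives no QALY horizon and no rule for utility after the last questionnaire.

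**The concern.** A QALY multiplies time alive by utility. Here the time component is observed for years and the utility component for one. Durability is one of the named comparisons between EVAR and its alternatives (Summary and section 1). Section 4.2 says that endoleak may need further procedures and affects both costs and patient anxiety. An admission for such a procedure in year 2 or 3 would enter the cost side, but any accompanying change in utility would not be measured.

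How to handle the gap analytically can be left to an analysis plan. Whether the data exist cannot: the collection schedule is fixed in the protocol, and questionnaires not given at years 2 to 4 cannot be obtained afterwards. At stake is the credibility of the cost-utility result. The mortality comparisons are unaffected.

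**Working it through.** **Inputs from the protocol.** Last EuroQol at 12 months (4.3, 4.5). Recruitment over 4 years in both trials (section 5). For Trial 2 (4.1): control mortality 25% per year, relative difference about 45%, 90% power, two-tailed alpha 1%, about 734 patient-years, to be met by 300 patients "assuming an average follow-up per patient of 2.5 years with a further minimum one year follow-up".

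**The plan's own figure.** Comparing 25% with 25% × (1 − 0.45) = 13.75%, two-sided alpha 0.01, power 0.90, no continuity correction, gives 365 per arm or 730 in total, against 734 stated. On the accrual side, 300 × 2.5 = 750. Both are close to 734, so the planned follow-up is understood correctly.

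**Share of life-years after 12 months.**

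Share = 1 − (mean time observed in year 1) / (mean total time observed)

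*Assumptions:* entry uniform over 4 years; exponential survival at annual rate h; follow-up closing at year 4 (potential follow-up F uniform on 0 to 4) or at year 5 (F uniform on 1 to 5). For a patient with potential follow-up F, the expected time observed is (1 − e^(−hF))/h, or F when h = 0. The time in year 1 replaces F by the smaller of F and 1. The short wait for treatment is ignored.

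*No deaths, closing at year 4:* mean total 2.0 years; year 1 holds 0.75 × 1 + 0.25 × 0.5 = 0.875; share = 1 − 0.875/2.0 = 56%.

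*No deaths, closing at year 5:* mean total 3.0; year 1 holds 1.0; share = 1 − 1/3 = 67%.

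*h = 0.25, closing at year 4:* mean total 1.47; year 1 holds 0.78; share = 47%.

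*h = 0.25, closing at year 5:* mean total 2.03; year 1 holds 0.88; share = 56%.

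| Annual death rate | Close at year 4 | Close at year 5 |
|---|---|---|
| 0 | 56% | 67% |
| 0.07 | 54% | 64% |
| 0.15 | 51% | 61% |
| 0.25 | 47% | 56% |

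The rates 0.07 and 0.15 are assumptions that fill in the range. If 25% is read as a yearly probability rather than a rate, the bottom row becomes 46% and 55%. At 30% yearly it is 43% and 52%.

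**Effect of adding years 2, 3 and 4.** Ignoring deaths, life-years after the last *planned* EuroQol fall from 56% to 0% (close at year 4), or from 67% to 0.125/3.0 = 4% (close at year 5). The gain in *actual* coverage is smaller. Closing at year 4, a patient whose follow-up ends between two annual visits has on average half a year after the last one. Counting only time after month 12, that is 0.75 × 0.5 = 0.375 year per patient, and 0.375/2.0 = 19% of life-years.

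Patients able to reach each visit, before deaths:

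| Visit | Close at year 4 | Close at year 5 |
|---|---|---|
| 2 years | 50% | 75% |
| 3 years | 25% | 50% |
| 4 years | almost none | 25% |

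**The case against.** The strongest reply is that a 12-month schedule is a legitimate choice. Section 4.3 aims for a short questionnaire, no passage contradicts the schedule, and the QALY horizon and any extrapolation belong in an analysis plan that is not shown. Later deaths, admissions and adverse events are recorded, so utility losses could be modelled from events, and section 4.4 promises wide sensitivity analysis. The cost-utility analysis is also conditional on its third scenario. All of this stands, and it is why the point is put conditionally. It does not remove the gap, because modelled decrements and sensitivity ranges for years 2 to 4 would have no trial utilities to inform them.

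A reader might infer four stronger things that the document does not support:

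- *That at least 60% of survival must be unmeasured in Trial 2*, from 1 − 1/2.5. This treats a planning average as person-time achieved. With deaths removed, the mean is about 2.0 years at a rate of 0.25 even when closing at year 5. If follow-up closes at year 4, the share can fall below half. Section 5 puts evaluation of the data in the fourth year, so that closure is a possible reading.
- *That the 12-month value will be carried forward.* No such rule is stated.
- *That device problems fall mainly after 12 months.* The protocol gives no distribution of their timing, and its early CT scans look for them from the first month.
- *That the result will favour a particular arm.* If the arms have similar utility at 12 months and stay so, the difference in QALYs is little affected however large the unmeasured share.

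It is also fair that adding the EuroQol alone leaves the anxiety inventory and the Patient Generated Index at 12 months, although section 4.4 relies on the latter because the EuroQol is less responsive.

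**Conclusion.** The point holds in conditional form. If the cost per QALY uses survival and costs beyond 12 months, about half to two-thirds of observed life-years have no measured utility, under uniform 4-year entry, exponential survival and the death rates shown. Mortality of 25-30% a year with closure at year 4 brings the share to 43-46%. If the horizon is instead 12 months, no extrapolation is needed, but the later deaths, costs and durability findings drop out of the economic result.

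These percentages measure how much survival lacks data. They are not an estimate of bias, whose size and direction cannot be derived from the document. The change is worth making because it is cheap now and cannot be made once patients have passed their later visits.

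**What to change.** In sections 4.3 and 4.5, add the EuroQol at 2, 3 and 4 years, as far as each patient's follow-up reaches, in all arms of both trials. It can be given at the annual follow-up already needed for CT and creatinine. The other questionnaires can stay at 12 months; whether to extend the Patient Generated Index is a separate choice.

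The cost is five items per annual follow-up and no extra visit. Section 3.7 already allows 20 minutes for a follow-up appointment and pays £25 for each complete set of follow-up data. The drawbacks are a small added burden on patients, some missing late forms, and relatively few contributors at 3 and 4 years because of staggered entry. The late estimates will therefore be imprecise, and some assumption about utility after each patient's last form will still be needed.
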